1 SYNOPSIS

Title	XEN 45 Gel Stent: Long Term Performance and Safety Assessment (XEN LT)
Protocol number	CMO-MA-EYE-0590
Clinical trials.gov Registration Number	Not yet registered
Planned study dates	Data extraction is planned to be conducted between fourth quarter 2018 and second quarter 2019.
Objectives	
Primary objective:
 
 The primary objective of this study is to assess the performance of XEN 45 Gel Stent over the long term as assessed by the change in intraocular pressure (IOP) compared to medicated IOP at baseline and the change in the number of topical IOP-lowering medications compared to baseline, 3 years after implantation. 
Secondary objectives:
 
 Assess the performance of XEN 45 Gel Stent over the long term as assessed by the change in IOP compared to medicated IOP at baseline and the change in the number of topical IOP-lowering medications compared to baseline, 4 years after implantation. Assess success over the long term following implantation of the XEN 45 Gel Stent^[a]. Assess safety over the long term following implantation of the XEN 45 Gel Stent 
[a] Qualified success of implantation of the XEN 45 Gel Stent will be defined as $\geq 20\%$ reduction from medicated baseline with no secondary surgical intervention (SSI) for glaucoma and no clinical hypotony (as defined in synopsis section "Data Collection and Procedures") while staying on same or fewer topical IOP-lowering medications than at baseline.
 
Complete success of implantation of the XEN 45 Gel Stent will be defined as $\geq 20\%$ reduction from medicated baseline with no SSI for glaucoma and no clinical hypotony while taking no topical IOP-lowering medications.

Study Design	This is a retrospective, non-interventional, observational, multi-center, chart review study to be conducted in patients who underwent placement of the XEN 45 Gel Stent as a standalone procedure or in combination with phacoemulsification from 1 January 2014 to 1 October 2015.
Rationale	XEN 45 Gel Stent performance and safety have been previously demonstrated in clinical trials designed for regulatory approval. However, studies conducted to date only provide data up to 2 years. This study will allow an assessment of the long-term performance and safety of the XEN 45 Gel Stent surgeries performed in Europe in typical clinical settings.

Duration of study	
Data extraction will cover the period from 1 January 2014 up to 1 October 2018.
 
For each eye selected, retrospective data available from baseline (i.e., day when decision was made to implant XEN 45 Gel Stent) until Last Visit (i.e., date of the last follow-up visit available prior to 1 October 2018 or date on which the patient had a SSI for glaucoma, whichever occurs first), will be extracted from existing medical records.

Patient Population and Key Selection Criteria	
The study population will include eyes treated with XEN 45 Gel Stent for open angle glaucoma as a standalone procedure or in combination with phacoemulsification between 1 January 2014 and 1 October 2015; and with documented post-operative follow-up available in the medical charts. For patients implanted bilaterally both eyes can be entered into the study database if they both meet eligibility criteria.

Sample Size	
This chart review study plans to accrue a minimum of 60 study eyes that have had at least 3 years of follow-up data after the initial implant with XEN 45 Gel Stent without a SSI for glaucoma. Based on data from the MS-001 trial, it has been assumed that mean IOP reduction at 3 years will be -5.6 (± 6.32) mmHg. The 95% confidence interval (CI) of the projected mean reduction afforded by a sample of 60 study eyes is -7.2 to -4.0 mmHg. That is, the half-length of the interval is 1.6 mmHg, which provides a reasonable precision for the estimate of the projected mean reduction in IOP.
 
Data collection for a study eye will stop at the Last Visit. While a precise sample size cannot be calculated, it has been assumed based on the 2-year outcomes from the MS-001 trial that selecting at least 150 eyes into the study will ensure that this chart review study will accrue a minimum of 60 study eyes with at least 3 years of follow-up data after the initial implant with XEN 45 Gel Stent.

Outcome Variables and Assessments	
Performance
 
 • Change in IOP from medicated baseline to 3 years after XEN 45 Gel Stent implantation • Change in IOP from medicated baseline to 4 years after XEN 45 Gel Stent implantation • Study pre-defined IOP outcomes achieved while staying on the same number or fewer IOP-lowering medications and without clinical hypotony: 20% reduction from medicated baseline, IOP below 12 mmHg, below 13 mmHg, ..., up to IOP below 18 mmHg • Change in the number of topical IOP-lowering medications from medicated baseline to 3 years after XEN 45 Gel Stent implantation • Change in the number of topical IOP-lowering medications from medicated baseline to 4 years after XEN 45 Gel Stent implantation • Qualified or complete success 3 years after XEN 45 Gel Stent implantation • Qualified or complete success 4 years after XEN 45 Gel Stent implantation

	
Safety
 
 Adverse events of special interest (AESIs) as defined below in the Section "Data Collection Procedures"

Study Procedures
	
Patients' medical charts will be extracted until the study target population has been reached. Site personnel will be required to complete a screening log for patients treated with XEN 45 Gel Stent on or after 1 January 2014 until 31 December 2014 to identify eligible patients. End date can be up to 1 October 2015 if the target number of eyes for the primary analysis has not been reached. For each eye selected, retrospective data will be extracted from existing medical records from XEN 45 Gel Stent implantation until 1 October 2018 or until the date on which the patient received a SSI for glaucoma, whichever occurs first. The study will not impose any separate patient visits at the site. In case key data are not available within the charts at the site, site personnel will be asked to liaise with the patients' treating ophthalmologist to request data to be made available for investigators for data entry.
 
When both eyes from the same patient meet eligibility criteria, each eye will be included in the study database with a unique identifier, and eyes will be paired in the electronic data capture system.


Data Collection Procedures
	
Screening Log
 
The following data concerning eyes treated at the site with XEN 45 Gel Stent during the period of interest will be extracted in anonymous screening logs. If both eyes of a patient had undergone XEN 45 Gel Stent implantation, one line should be completed in the screening log per treated eye.
 
 Eye in which XEN 45 Gel Stent was implanted (Oculus Dexter vs. Oculus Sinister) Indication for XEN 45 Gel Stent implantation Date (MM YYYY) of XEN 45 Gel Stent implantation Date (MM YYYY) of Last Visit Reason why the patient has not been selected for the study, if applicable 
Case Report Form
 
The following data concerning eye treatment and clinical condition will be collected chronologically for eligible eyes at the indicated time points.
 
Baseline is defined as the day when the decision was made to implant XEN 45 Gel Stent. For each selected eye, all retrospective data available from baseline until Last Visit, will be extracted from existing medical records.
 
 Demographics at baseline (age, race and gender) 
 Ocular and glaucoma medical history: glaucoma diagnosis and stage, previous ocular and glaucoma procedures, previous ocular medications (including whether or not eye is treated with Diamox on

	
the day when decision was taken to implant XEN 45 Gel Stent) and ocular pathologies observed at baseline.
 
 • Surgery data: anti-metabolite and/or anti-fibrotic used prior to XEN 45 Gel Stent implantation, procedure performed (i.e., XEN 45 Gel Stent implantation alone or phacoemulsification + XEN 45 Gel Stent implantation), XEN 45 Gel Stent and cataract-related complications, and if available surgical notes • IOP data: IOP and number of IOP-lowering medications at baseline and at all data collection points defined for the study period. • Eye assessment: visual field exam and best corrected visual acuity at all data collection points defined for the study period. • Dates of needling procedures • SSI for glaucoma: nature and date • AESIs: 
 ○ Anterior chamber defects (shallow with peripheral iridocorneal touch; flat with irido-corneal touch extending to the pupil); ○ Bleb leak; ○ Blebitis; ○ Choroidal effusion, hemorrhage or mixed effusion hemorrhage (extending posterior to the equator, with or without blood; obscuring disc or macula, with or without blood; with choroids touching in the center of the eye, with or without blood); ○ Corneal decompensation (transient i.e. <30 days or persistent i.e. >30days); ○ Endophthalmitis; ○ Hyphema (≥ 2 mm in height (layered) at any time; present or arising > 30 days postoperatively); ○ Persistent Hypotony (IOP < 6 mmHg, present at two consecutive visits postoperatively > 30 days apart); ○ Clinical Hypotony (vision reduction (2 lines or more) related to macular changes consistent with hypotony maculopathy (macular folds), optic disc edema, and/or serious choroidal detachments because of low IOP ○ Implant blockage; ○ Implant exposure or extrusion / conjunctival erosion; ○ Implant migration; ○ Implant repositioning requiring surgical intervention; ○ Implant touching iris or cornea; ○ Iritis (requiring treatment after the postoperative medication taper); ○ Macular edema; ○ Retinal detachment; ○ Suture abscess or other local infection; ○ Vitreous hemorrhage;
--	---

	
 ○ And any other adverse event that leads to permanent visual impairment or requires surgical or medical intervention to prevent permanent visual impairment

Statistical Methods
	
Analysis Populations
 
Data will be presented for all eyes selected and meeting the selection criteria, i.e. Analysis Population. Additional groups may be also examined, as deemed appropriate (e.g. eyes that did or did not undergo phacoemulsification).
 
Primary Objective
 
Change in IOP from medicated baseline and change in the number of topical IOP-lowering medications compared to baseline will be summarized descriptively at Year 3 after XEN 45 Gel Stent implantation in eyes from the Analysis Population with at least 3 years of follow-up data and were not treated with Diamox on the day when decision was taken to implant XEN 45 Gel Stent.
 
Secondary Objectives
 
Change in IOP and Number of Topical IOP-Lowering Medications at 4 Years after XEN 45 Gel Stent Implantation
 
Change in IOP from medicated baseline and change in the number of topical IOP-lowering medications compared to baseline will be summarized descriptively at Year 4 after XEN 45 Gel Stent implantation in eyes from the Analysis Population with at least 4 years of follow-up data and were not treated with Diamox on the day when decision was taken to implant XEN 45 Gel Stent.
 
Success over the Long Term of Implantation of the XEN 45 Gel Stent
 
Number and proportion of eyes achieving a 20% reduction in IOP from medicated baseline, and number and proportion of eyes with an IOP <18 mmHg, IOP <17 mmHg, ..., down to IOP<12 mmHg will be described at all data collection time-points in eyes from the Analysis Population that did not underwent SSI for glaucoma, did not have clinical hypotony, and were not treated with Diamox on the day when decision was taken to implant XEN 45 Gel Stent.
 
The number and proportion of eyes achieving "success" at 3 and 4 years after XEN 45 Gel Stent implantation will be summarized descriptively. Analyses will be conducted in the Analysis Population. Kaplan-Meier analyses will be conducted to analyze time from initial procedure to SSI for glaucoma.
 
Safety over the Long Term of Implantation of the XEN 45 Gel Stent
 
Surgical complications and post-operative AESIs will be summarized descriptively using frequencies and percentages. Analyses will be performed in the Analysis Population.

The study shall be conducted in compliance with the ethical principles arising from the Declaration of Helsinki revised in 2013, ISO-14155-2011, European and National laws in terms of data protection, and the Guidelines on Medical Devices: Post Market Follow-Up Studies- a Guide for Manufacturers and Notified Bodies (MEDDEV 2.12/2 rev 2).

2 LIST OF ABBREVIATIONS

Abbreviation	Definition
AE	Adverse event
AESI	Adverse event(s) of special interest
BCVA	Best corrected visual acuity
CI	Confidence interval
CRA	Clinical research associate(s)
CRO	Contract research organization
EC	Exclusion criteria
eCRF	Electronic case report form
EDC	Electronic data capture
EDTRS	Early Treatment Diabetic Retinopathy Study
IC	Inclusion criteria
IEC	Independent ethics committee
IOP	Intra-ocular pressure
ISO	International Organization for Standardization
LogMAR	Logarithm of Minimum Angle of Resolution
MEDDEV	European Medical Device Vigilance System
MedDRA	Medical dictionary for regulatory activities
MIGS	Minimally invasive glaucoma surgery
OD	Oculus dexter
OS	Oculus sinister
SAE	Serious adverse event
SAP	Statistical analysis plan
SD	Standard deviation
SSI	Secondary surgical intervention
WHO	World Health Organization

3 STUDY MILESTONES AND TIMELINES

The planned study milestones and timelines are described in Table 1 below.

Table 1 Study Milestones and Timelines

Milestone	Estimated Date
Ethics submission	Third quarter 2018
Start of data collection	Fourth quarter 2018
End of data collection	Second quarter 2019
Final Report of study results	Third quarter 2019

4 AMENDMENTS AND UPDATES

This section is not applicable (original protocol).

5 INTRODUCTION

5.1 Background

The term “glaucoma” refers to a group of diseases that have in common a characteristic damage to the optic nerve with associated visual field loss. Glaucoma is the second leading cause of blindness worldwide; blindness from glaucoma is irreversible. Glaucoma can occur in all age groups including infants, but it is most common in elderly people (Glaucoma Panel, 2016). Other risk factors include race with estimated prevalence being six times higher for certain age groups in black American populations, a steepest increase in open-angle glaucoma with age in white populations compared to black American populations, and a higher incidence of primary angle-closure glaucoma in Asian populations compared to white patients (McMonnies, 2016). There are two major types of glaucoma, primary open-angle glaucoma and primary angle-closure glaucoma.

The goal in the treatment of glaucoma is to prevent further loss of functional vision and to avoid an adverse impact on the patient’s quality of life (Glaucoma Panel, 2016). Glaucoma is a chronic progressive disease that requires continuous long-term cooperation of the patient with the glaucoma management proposed by the doctor. Currently, the only approach proven to be efficient in preserving visual function is lowering intra-ocular pressure (IOP) (Heijl et al., 2002) as elevated IOP is recognized as the primary risk-factor for glaucoma. IOP is lowered using medications, laser therapy or incisional surgery. Medical treatment is usually initiated as a first step in most cases. However, non-adherence to treatments dosed daily is common in glaucoma and has been linked to poor outcomes in vision-related quality of life (Thompson et al., 2018). Laser therapy is generally efficient in the first few months after treatment initiation, but has been shown to lose efficiency in the long term (Wienreb et al., 1995). Incisional surgeries can be defined as an attempt to lower IOP by the surgical formation of an artificial drainage pathway from the anterior chamber to the subconjunctival space (Lewis et al., 2014). Although several techniques have been developed to provide subconjunctival drainage, too many short- and long-term complications are still associated with this surgery, as over-filtration results in hypotony and under-filtration due to scarring in surgical failure (Watson et al. 1990).

More recently, several medical devices have been developed to treat glaucoma. The term “Minimally invasive glaucoma surgery” (MIGS), defined in a joint meeting of the American Glaucoma Society and US Food and Drug Administration (Caprioli et al., 2015), refers to a group of devices that are significantly less invasive and offers a new perspective of IOP reduction with less risk, short operating times and rapid recovery. The three main approaches of IOP reduction by MIGS devices include increasing trabecular–Schlemm’s canal outflow (iStent, Hydrus Microstent), increasing uveoscleral outflow via uprachoroidal pathways (CyPass Micro-Stent), or creating a subconjunctival drainage pathway (XEN 45 Gel Stent) (Richter et al., 2016).

XEN 45 Gel Stent (Allergan Inc.) is an *ab interno* gelatin stent implanted via a clear corneal incision without conjunctival incision and is the only available filtering micro-invasive glaucoma surgery device that allows the subconjunctival filtration. The stent is intended to be implanted in the angle and through the sclera, connecting the anterior chamber to the subconjunctival space. It is a tube with an inside diameter of approximately 45 µm, its outside diameter is approximately 150 µm,

and it is approximately 6 mm long in its dry state. The gelatin imparts hydrophilic properties that allow the tube to expand when hydrated by contact with aqueous fluid. This expansion of the outer diameter of the tube aids in keeping the gelatin stent in its intended location after surgical implantation. The implant is housed in a disposable preloaded handheld inserter designed specifically for surgical implantation. The XEN 45 Gel Stent is intended to reduce intraocular pressure in patients with primary open angle glaucoma where previous medical treatments have failed (XEN 45 Gel Stent direction for use). The performance and safety of XEN 45 Gel Stent has been previously demonstrated in a few clinical trials. IOP reduction one year after XEN 45 Gel Stent has been shown to vary between 23% and 41% (Galal et al., 2017; De Gregorio et al., 2017; Mansouri et al., 2018, Perez-torregrosa et al. 2016, Stalmans and Vera, 2017). In a larger retrospective study including 242 eyes, decrease in IOP one year after XEN 45 Gel Stent implantation reached 54.1% (Hengerer et al., 2017) with a reduction in the number of IOP medication from approximately 3 before XEN 45 implantation to 0.3 one year after stent implantation. One prospective, multi-center, open-label trial, the MS-001 Trial, collected data over the 2 years following XEN 45 Gel Stent implantation (data not yet available). Overall, these studies demonstrated a good safety profile of XEN 45 Gel Stent with a relatively low number of events. Most common complications that may occur in conjunction with the use of XEN 45 Gel Stent include, but are not limited to, choroidal effusion, hyphema, hypotony, implant migration, implant exposure, wound leak, need for secondary surgical intervention (SSI) and other known complications of intraocular surgeries (e.g. flat or shallow chamber, corneal edema, endophthalmitis) (XEN 45 Gel Stent label).

5.2 Study Rationale

XEN 45 Gel Stent performance and safety have been previously demonstrated in clinical trials designed for regulatory approval. However, studies conducted to date only provide data up to 2 years. This study will allow an assessment of the long-term performance and safety of the XEN 45 Gel Stent surgeries performed in Europe in typical clinical settings.

6 OBJECTIVES AND OUTCOME VARIABLES

6.1 Objectives

6.1.1 Primary objective

The primary objective of this study is to assess the performance of XEN 45 Gel Stent over the long term as assessed by the change in IOP compared to medicated IOP at baseline and the change in the number of topical IOP-lowering medications compared to baseline, 3 years after implantation.

6.1.2 Secondary objective

The secondary objectives of this study are to:

- Assess the performance of XEN 45 Gel Stent over the long term as assessed by the change in IOP compared to medicated IOP at baseline and the change in the number of topical IOP-lowering medications compared to baseline, 4 years after implantation.
- Assess success over the long term following implantation of the XEN 45 Gel Stent as defined in Section 6.2.
- Assess safety over the long term following implantation of the XEN 45 Gel Stent.

6.2 Key Variable Definitions

Qualified success of implantation of the XEN 45 Gel Stent will be defined as $\geq 20\%$ reduction from medicated baseline with no SSI for glaucoma and no clinical hypotony while staying on the same number or fewer topical IOP-lowering medications than at baseline.

Complete success of implantation of the XEN 45 Gel Stent will be defined as $\geq 20\%$ reduction from medicated baseline with no SSI for glaucoma and no clinical hypotony while taking no topical IOP-lowering medications.

6.3 Outcome Variables

Performance outcomes:

- Change in IOP from medicated baseline to 3 years after XEN 45 Gel Stent implantation
- Change in IOP from medicated baseline to 4 years after XEN 45 Gel Stent implantation
- Study pre-defined IOP outcomes achieved while staying on the same number or fewer topical IOP-lowering medications and without clinical hypotony: 20% reduction from medicated baseline, IOP below 12 mmHg, IOP below 13 mmHg, ..., up to IOP below 18 mmHg
- Change in the number of topical IOP-lowering medications from medicated baseline to 3 years after XEN 45 Gel Stent implantation
- Change in the number of topical IOP-lowering medications from medicated baseline to 4 years after XEN 45 Gel Stent implantation
- Qualified or complete success 3 years after XEN 45 Gel Stent implantation

- Qualified or complete success 4 years after XEN 45 Gel Stent implantation

Safety outcomes:

- Adverse events of special interest (AESIs), as defined in Section 10.9.2.

7 STUDY CONDUCT

7.1 Overall Design of the Study

This is a retrospective, non-interventional, observational, multi-center, chart review study to be conducted in patients who underwent placement of the XEN 45 Gel Stent as a standalone procedure or in combination with phacoemulsification from 1 January 2014 to 1 October 2015. For patients implanted bilaterally, both eyes can be entered into the study database if they both meet eligibility criteria. Data from approximately 150 eyes will be collected by retrospective review of medical charts in 5 European countries. Countries considered at time of protocol development are: Austria, Belgium, Germany, Spain and the United Kingdom. Sites will be centers with certified XEN 45 Gel Stent surgeons known to have implanted XEN 45 Gel Stent in the time period being studied.

Patients' medical charts will be extracted until the target number of eyes for the primary analysis has been reached. Site personnel will be required to complete a screening log for patients treated with XEN 45 Gel Stent on or after 1 January 2014 to identify eligible patients (see Section 9.2). For each eye selected, all retrospective data available from baseline (i.e. day when decision was made to implant XEN 45 Gel Stent) until Last Visit (i.e. date of the last follow-up visit available prior to 1 October 2018 or date on which the patient had a SSI for glaucoma, whichever occurs first) will be extracted from existing medical records. The study will not impose any separate patient visits to the site. In case key data are not available within the charts at the site, site personnel will be asked to liaise with the patients' treating ophthalmologist to request data to be made available for investigators for data entry.

A feasibility assessment will be conducted prior to the study conduct in the considered countries to assess whether targeted sites have access to complete patient records including patient's follow up after implantation of XEN 45 Gel Stent, to assess the number of eligible eyes, and to assess sites willingness to participate in the study.

If both eyes from the same patient meet eligibility criteria, each eye will be included in the study database with a unique identifier and eyes will be paired in the electronic data capture system (EDC). Study procedures, and evaluations are described in detail in Sections 9 and 10 and data to be collected are summarized in Table 2: surgery data (procedure performed, XEN 45 Gel Stent and cataract related complication, anti-metabolite and/or antifibrotic therapy used), IOP level, number of topical IOP-lowering medications taken, eye examination (visual field exam, best corrected visual acuity...), interventions performed on the study eyes, IOP lowering medications, and AESIs. Safety events to be collected are described in Section 10.9.

Data extraction may begin as soon as sites are initiated. This study will collect anonymized data (i.e. no list of identifier will be kept by the sites and once data are entered in the system, investigators, study personnel and sponsor will not be able to identify patients), therefore no informed consent will be requested from patients.

Table 2 displays the time frame during which study variables will be collected.

Table 2 Schedule of Data Collection

Data Collected	Baseline^[a]	XEN 45 Gel Stent Implantation	Study Period^[b]
Eligibility Assessment	X		
Demography	X		
Ocular and Glaucoma Medical History	X		
Surgery-related data		X	
Number of IOP-lowering medications	X		X
Visual field exam^[c]	X		X
Intraocular pressure	X		X
Best corrected visual acuity	X		X
Needling procedures			X
Secondary surgical intervention for glaucoma			X
Adverse events of special interest			X

IOP=intra-ocular pressure.

[a] Baseline is defined as the day when the decision was made to implant XEN 45 Gel Stent.

[b] The study period is defined as the period between XEN 45 Gel Stent implantation and 1 October 2018. For each eye selected, all retrospective data available from baseline until 1 October 2018 or until the date on which the patient received a SSI for glaucoma, whichever occurs first, will be extracted from existing medical records.

[c] If no visual field exam is available at baseline, a value measured up to 12 months prior to baseline is acceptable. In the event that more than one value is available in this 12-month period, the value closest to the baseline date will be used.

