8.2.3 Minimum Required Dataset

Medical charts that do not include the following data will not be selected for the study. Therefore, if no data is available within the charts at the study site, before selecting the chart for inclusion in the study it must be established that certain key data from other locations will be made available for investigators for data entry.

Patient characteristics

- Age
- Gender

Intraocular Pressure

- IOP at baseline (i.e. medicated IOP) and until last visit (1 October 2018 or until the date on which the patient received a SSI for glaucoma, whichever occurs first)
- Number of topical IOP-lowering medication prescribed for the study eye at baseline and until last visit (1 October 2018 or until the date on which the patient received a SSI for glaucoma, whichever occurs first)

Secondary surgical intervention

- Date of the SSI for glaucoma, if any

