10 STUDY ASSESSMENTS

10.1 Data Collected in the Screening Log

Once a site has been initiated, site personnel will be required to complete an anonymized screening log with all patients' eyes that underwent XEN 45 Gel Stent implantation as described in Section 9.2. If both eyes of a patient had undergone XEN 45 Gel Stent implantation, one line should be completed in the screening log per treated eye. For all screened patients' eyes, the data listed in Table 3 will be collected to help site personnel identify eligible eyes.

Table 3 Data Collected in Screening Logs

Data Collected	Selection Criteria
• Eye in which XEN 45 Gel Stent was implanted (OD vs. OS)	N/A
• Indication for XEN 45 Gel Stent implantation	IC1
• Date (MM YYYY) of XEN 45 Gel Stent implantation	IC2
• Date (MM YYYY) of Last Visit ^[a,b]	IC2
• Reason why the patient has not been selected for the study (did not meet selection criteria, lack of time, quotas were met, insufficient access to complete medical records, etc.)	N/A

IC=Inclusion criteria; N/A=not applicable; OD=oculus dexter; OS=oculus sinister

[a]. Last Visit is defined as the date of the last follow-up visit available prior to 1 October 2018 or date on which the patient had a SSI for glaucoma, whichever occurs first.

[b] Automated calculation will be implemented in the screening log to verify whether Last Visit occurred at least 3 years after XEN 45 Gel Stent implantation

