10.8 Secondary Surgical Intervention

If a SSI for glaucoma was performed on the study eye during the study period, the nature and date of the SSI will be collected. SSIs for glaucoma include but are not limited to trabeculectomy, table shunt, second gel stent, i-Stent, GATT, ABiC, and transscleral cycloablative procedures.

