1.6. Study Design

This is a retrospective, non-interventional, observational, multi-centre, chart review study conducted in patients who underwent placement of the XEN 45 Gel Stent as a standalone procedure or in combination with phacoemulsification from 1 January 2014 to 1 October 2015.

For each eligible eye, all retrospective data available from baseline (i.e. day when decision was made to implant XEN 45 Gel Stent) until Last Visit (i.e. date of the last follow-up visit available prior to 1 October 2018 or date on which the patient had a SSI for glaucoma, whichever occurs first) are extracted from existing medical records into the electronic CRF (eCRF) in Dacima.

If both eyes from the same patient meet eligibility criteria, each eye is included in the study database with a unique identifier and eyes are paired in the electronic data capture system (EDC). See section 4 for how bilateral eyes included in the study are handled in the analyses.

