4.6. Secondary surgical intervention

The median time for a patient in the Safety Population to have an SSI will be described by Kaplan-Meier curves. A summary of patients with SSI will be recorded by the time windows described in Section 4.1.

7. References

1. Glaucoma Panel. *Preferred practice pattern for primary open-angle glaucoma*. San Francisco 2006.

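### Extraction is worded to end at the patient's SSI rather than the study eye's; read literally, it cuts off the SSI-free eye of a bilateral patient

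*Protocol*

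**What the plan says.** The stopping rule is worded by patient wherever it appears:

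- Protocol Table 2, footnote b, ends extraction for each selected eye on 1 October 2018 or "until the date on which the patient received a SSI for glaucoma, whichever occurs first". The synopsis and the text of section 7.1 use equivalent wording.
- Protocol 8.2.3 requires IOP and medication data up to the last visit, with the alternative endpoint "until the date on which the patient received a SSI for glaucoma". The medication item refers to drugs prescribed for the study eye, so one bullet uses both units.
- The first footnote of protocol Table 3 defines Last Visit in the same patient-level terms. Footnote b of that table uses this Last Visit in an automated check of whether 3 years have passed since implantation.
- SAP 1.6 repeats the rule ("date on which the patient had a SSI for glaucoma, whichever occurs first"), and so does footnote b of the data collection table in SAP 1.8.

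SSI itself is specified by eye. Protocol 10.8 reads "If a SSI for glaucoma was performed on the study eye during the study period, the nature and date of the SSI will be collected". The sample-size target in 14.1 counts study eyes without an SSI. Protocol 14.2.5.2 and SAP 4.4.1 analyse eyes that had no SSI. SAP section 4 defines the Safety Population as eyes, but SAP 4.6 then describes "The median time for a patient in the Safety Population to have an SSI".

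Both eyes of a bilateral patient can be entered, each with its own identifier (protocol 7.1). Neither document says whether an SSI in the other eye ends extraction for the study eye.

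**The concern.** Take a patient with two study eyes whose right eye has a trabeculectomy at Month 10 while the left eye does well. A site that follows the words stops extracting the left eye at Month 10 and enters that date as its Last Visit. Three things follow for the left eye:

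- It has no Month 36 or Month 48 IOP or medication count, and no AESI is recorded after Month 10.
- It fails the 3-year check, and so drops out of the protocol's primary analysis, which requires at least 3 years of follow-up.
- Its time to SSI is censored at Month 10. The SAP gives no separate censoring rule, so Last Visit is the only defined end of follow-up.

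The trigger is glaucoma surgery in the same patient, so the loss could be related to prognosis. A second site might read the rule as applying to the study eye and extract the left eye in full, so comparable eyes would be handled differently across sites. Neither problem can be corrected after entry: sites keep no list of identifiers (protocol 7.1), and no queries are issued (protocol 12 and 14.3.3).

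**Working it through.** **The plan's own figure.** Inputs from protocol 14.1: mean change −5.6 mmHg, SD 6.32, n = 60.

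- Half-length = 1.96 × 6.32 / √60 = 1.599, i.e. 1.6 mmHg.
- Interval = −5.6 ± 1.6 = −7.2 to −4.0 mmHg. This agrees with the protocol and does not depend on how the stopping rule is read.
- Expected yield at the 30% loss taken from MS-001: 150 × 0.70 = 105 eyes, against the 60 required.

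**Paired eyes.** The documents give no bilateral share for this study. As an assumption, take that of MS-001 (protocol 14.1: 218 eyes in 199 patients).

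- Patients with two study eyes: 218 − 199 = 19.
- Share of eyes that are paired: 38/218 = 17.4%.
- Applied to 150 eyes: 150 × 0.174 ≈ 26 paired eyes, i.e. 13 bilateral patients.

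**Eyes cut off under the literal reading.** The documents give no SSI risk either. Assume a 3-year risk p per eye of 10–30%, independent between eyes. An eye is wrongly cut off if it has no SSI and its paired eye has one. The expected number is 26 × p × (1 − p) among all eyes and 13 × p × (1 − p) among primary eyes (the first-implanted eye, SAP section 4).

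| p | All eyes | Primary eyes |
|---|---|---|
| 0.10 | 26 × 0.09 = 2.3 | 13 × 0.09 = 1.2 |
| 0.20 | 26 × 0.16 = 4.2 | 13 × 0.16 = 2.1 |
| 0.30 | 26 × 0.21 = 5.5 | 13 × 0.21 = 2.7 |

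Positive correlation between a patient's two eyes would lower these counts, because fewer pairs would be discordant.

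**Effect on precision.** Among eyes that are themselves SSI-free, the share cut off is 0.174 × p.

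- p = 0.10: 1.7% lost. 60 eyes become 60 × 0.983 = 59.0; half-length = 1.96 × 6.32 / √59.0 = 1.61 mmHg.
- p = 0.30: 5.2% lost. 60 eyes become 60 × 0.948 = 56.9; half-length = 1.96 × 6.32 / √56.9 = 1.64 mmHg.

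Starting from the 105 eyes expected at 30% loss, the same shares leave about 103 and 99.5 eyes, still well above 60.

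**The case against.** The best defence is that the study eye is what the authors meant. The stopping rule sits in sentences about each selected eye, protocol 7.1 refers the reader to sections 9 and 10 for detail, and section 10.8 there is explicit: "If a SSI for glaucoma was performed on the study eye during the study period". The documents also use patient loosely for eye elsewhere. SAP 1.7 lists criteria for patients of which the first describes an eye, and Table 3 has one line per treated eye but asks why the patient was not selected. Sites receive training, an initiation call and telephone support, so a doubtful case can be raised before entry. Finally, selection continues until the target is reached, and the numbers are small: applying the 40–70% retention implied by 14.1 (60/150 to 0.70) to the primary eyes gives 1.2 × 0.40 = 0.5 to 2.7 × 0.70 = 1.9 eyes at Month 36.

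Most of this stands, and it makes the point an ambiguity rather than an established practice. It does not remove it. The words the site applies to Last Visit name the patient every time, no section settles the fellow-eye case, and the SAP repeats the wording.

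Three stronger readings are tempting but not supported:

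- *The fellow eye's own XEN counts as a second gel stent and ends follow-up of the first eye.* The list of procedures in 10.8 directly follows the sentence limiting SSI to the study eye. Protocol 9.2 has sites extract the second eye whatever its implantation date, and the SAP makes the first-implanted eye the primary eye. This reading would defeat both arrangements.
- *Glaucoma surgery in a fellow eye outside the study also ends follow-up.* Without an earlier XEN in that eye, such surgery is not evidently secondary.
- *Cut-off eyes would be counted as SSI events in the Kaplan-Meier curve.* Section 10.8 collects SSI on the study eye only, so early censoring is the expected error.

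**Conclusion.** The wording is at fault and should be corrected. The rule that ends extraction and sets Last Visit is stated by patient, while SSI is collected and analysed by eye. Applied as written, it cuts off SSI-free eyes of bilateral patients. It cannot be inferred that sites will in fact do this, since the eye-level sections point to the study eye as the intent. What the documents do support is that sites could differ and that the resulting loss could not be recovered.

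The size is about 2–5 of 150 eyes, or 1–3 primary eyes. This rests on three assumptions: the MS-001 bilateral share, a 3-year SSI risk of 10–30% per eye, and independence between eyes. The half-length moves from 1.60 to at most about 1.64 mmHg, and no sample-size figure changes. That the loss is related to prognosis is plausible, but neither its direction nor its amount can be shown from the documents. The case for the change is consistent extraction and correct follow-up time, not precision.

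**What to change.** In every Last Visit and study-period definition, replace the reference to the patient's SSI with *the study eye underwent a SSI for glaucoma*. The places are the protocol synopsis, 7.1, Table 2 footnote b, 8.2.3 and Table 3 footnote a, and SAP 1.6 and 1.8 (footnote b). Add one sentence stating that surgery on the fellow eye does not end extraction for the study eye. In SAP 4.6, define time to SSI per eye.

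The cost is a wording change in both documents and one line in the eCRF manual. It needs no extra charts and no change to the sample size. It helps only eyes not yet entered, and SAP 1.8 describes collection as under way. For pairs already in the database, the pairing in the EDC allows a simple check: list each SSI-free eye whose last extracted date coincides with the SSI date of its paired eye, and report the number.
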